4. STUDY PROCEDURES

4.1. Screening/Baseline Visit Procedures:

Potential participants will be initially screened for eligibility through a separate screening protocol (IRB#98-0799).

Within 12 months of completing the screening protocol, they will return for Visit 1. Sensitization to cat as determined by skin testing or IgE levels is not expected to change over the course of 12 months. Participants will have to meet all eligibility criteria at the time of the Baseline Visit. On Visit 1:

1. Consent will be obtained
2. Review of subject's medical history and current medications. Allergy skin prick test results from screening protocol #98-0799 will be included in the history.
3. Vital sign measurements (temperature, pulse, respiratory rate, blood pressure), oxygen saturation, and symptom scoring
4. Urine pregnancy test for women of child bearing potential
5. eNO
6. Spirometry
7. Venipuncture for CBC with Diff, Total and cat hair IgE, cytokines, and gene expression (approximately 50 cc total)
8. Physical exam of the ears, nose, throat and chest
9. Sputum induction
10. Collect nasal epithelial lining fluid (ELF).

After completion of the baseline visit, and if for any reason that subject cannot return for the challenge session in the required time, a repeat baseline visit will be done. At this visit the subject will repeat the following:

1. review history and meds
2. vitals
3. UPT
4. eNO
5. spirometry
6. PE

If more than 2 months has elapsed after the original baseline visit, or if the visit was rescheduled due to illness in the participant, the blood work will also be repeated. Subjects must continue to meet all other study inclusion criteria.

4.2. Intervention/Treatment procedures

Visit 2: Methacholine Challenge Day (at least 2 days but less than 2 weeks after the baseline visit V1)

1. Review any change in medical status since last visit
2. Vital signs, oxygen saturation, and symptom score
3. Urine pregnancy test
4. Baseline HRV measurement
5. eNO
6. Spirometry
7. Physical exam of the ears, nose, throat and chest

8. Methacholine challenge if inclusion and exclusion criteria are still met (refer to section 5.4 for methacholine challenge procedure)

Visit 3: Allergen challenge day (24-48 hours after V2)

1. Review any change in medical status since last visit
2. Vital signs, oxygen saturation, and symptom score
3. Placement of the HRV device
4. Placement of the ASSIST devices (cardiac electrodes and wrist band)
5. eNO
6. Collect nasal ELF
7. Spirometry
8. If inclusion and exclusion criteria are still met, allergen challenge will be performed as described in section 5.1.
 - a. If subject is asymptomatic and FEV1 drops $<10\%$ at the completion of allergen challenge, subjects will be monitored for 2 hours post challenge and will be discharged following post-challenge venipuncture with rescue medications (albuterol with aerochamber and oral prednisone 60 mg), instructions for use of these medications if asthma symptoms occur, and contact information for the on-call physician. Subject will resume protocol beginning with Study visit 4 detailed below.
 - b. Any subject whose FEV1 drops $\geq 10\%$ will stay for the 10 hour post-allergen monitoring period as outlined below.
9. Collect nasal ELF after completion of the allergen challenge, either following the dose producing a 20% or greater fall in FEV1 (in early phase responders) or following completion of the highest dose of inhaled allergen (in those who do not exhibit an early phase response).
10. Post-challenge monitoring of vital signs every 10 minutes for the 1st hour, then every 30 minutes until 2 hours post-challenge, then hourly until 10 hours post-challenge
11. Spirometry when vital signs are obtained
12. eNO hourly between 2 and 10 hours post-challenge
13. Collect nasal ELF at 7 hours post-challenge (7 hours after the onset of the early phase response).
14. Venipuncture for CBC with diff, cytokines, and gene expression 10 hours post-challenge (approximately 50 cc total)
15. All subjects will receive 4 puffs of albuterol 10 hours post-challenge. Spirometry will be performed 15 minutes after albuterol if post-challenge FEV1 at 10 hours was not approximately within 10% of baseline.
 - a. Albuterol will be repeated every 20 minutes up to three doses if repeat FEV1 is not within approximately 10% of baseline value or if subject remains in distress.
 - b. If needed, after three inhaled albuterol treatments, additional medications, including nebulized albuterol, atrovent and oral prednisone 60mg, will be given per physician discretion.
16. Subjects will be discharged 10 hours following allergen challenge when clinically stable and when FEV1 is within approximately 10% of baseline FEV1. HRV monitoring will be discontinued prior to discharge. At discharge, all subjects will be provided with an albuterol inhaler and aerochamber, a single dose of oral prednisone 60 mg, clear instructions for use of rescue medications in the event of symptoms related to bronchoconstriction, and contact information for the on-call physician. Subjects will reside overnight at their home if their residence is within 10 miles of UNC or a local hotel within 10 miles of UNC.

Visit 4: 24 hours post challenge

1. Vital signs, oxygen saturation, and symptom score
2. eNO
3. Spirometry
4. Venipuncture for CBC with Diff, gene expression, cytokines (approximately 50 cc total).
5. Methacholine challenge.
6. Sputum induction.
7. Collect nasal ELF.

4.3. Follow up Procedures

Post Challenge Observations/Reporting

1. Subjects will be contacted for phone call follow-up 24 hours after post-challenge sputum induction (see phone script included in the study worksheets section)
2. Each volunteer will be given a symptom scoring sheet for each day up to 96 hours (4 days) after challenge (see symptom scoring sheet in section 5.8.).
3. Any subject who requires a dose of an oral corticosteroid (prednisone 60 mg) for treatment of asthma symptoms will be contacted by phone within 24 hours of the dosing to assess asthma symptoms. These subjects will return to the research lab within 48-72 hours of the dose for FEV1, symptom scoring and physical exam by a study physician to assess need for continued steroid treatment.

Study discontinuation visit within 10 days of the final challenge dose:

1. Vital signs, oxygen saturation, and symptom score
2. Spirometry
3. eNO
4. If any findings are abnormal, medical evaluation as directed by the study physician will be undertaken.

4.4. Unscheduled Visits

We do not anticipate any unscheduled visits. If the subject is determined to be too ill to participate in the study visit procedures, then their research visit will be rescheduled after resolution of illness.

4.5. Concomitant Medication Documentation

Medication review will be obtained by a study coordinator at each study visit and documented in the participant's paper chart.

4.6. Rescue Medication Administration

Albuterol (via metered dose inhaler) will be available at all times during the allergen challenge and throughout the study visits. Albuterol will be administered any time the participant requests it for respiratory symptoms. Additionally, 4 puffs of albuterol will be administered if the participant experiences a 40% or greater decrease in FEV1 or FVC from pre-challenge values during the allergen challenge.

All subjects will receive 4 puffs of albuterol 10 hours after allergen challenge. If clinically stable and if FEV1 is approximately within 10% of baseline pre-challenge FEV1, subject will be discharged with an albuterol inhaler with aerochamber and a single oral dose of prednisone 60 mg, clear instructions on use of medications in the event of symptoms related to bronchoconstriction, and contact information for the on-call physician. If FEV1 has not recovered to within 10% of baseline pre-challenge values by 10 hours after the allergen challenge, 4 puffs of albuterol will be administered, and spirometry will be repeated 15 minutes later.

If the subject requires albuterol for 48 hours or longer after the inhaled allergen challenge, they will be instructed to begin a single dose of prednisone 60 mg and continue following instructions from the provided asthma action plan for albuterol use. If the subject is instructed to begin prednisone treatment, the team will contact the subject 24 hours after initiation to assess their symptoms and identify if the subject needs to be seen in the research clinic that day. Subjects who require a dose of prednisone will be seen in the research lab 48-72 hours after the dose to assess the need for a full course of oral corticosteroids.

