1.3. Non-Clinical and Clinical Study Findings

The study agent is commercially available for use in allergen immunotherapy (allergy shots) for patients with allergic rhinitis triggered by cat exposure. Inhaled cat allergen protocols have been used to reliably, reproducibly, and safely induce mild bronchoconstriction in allergic asthmatics and serve as a model of allergen-induced asthma exacerbation, which can be used to test asthma therapies targeting specific components of this inflammatory response¹⁷⁻²⁰. The cat hair extract inhalation protocol was adapted from a published study by Sicherer et al¹⁸ as well as from our existing protocol for house dust mite extract inhalation (IND# 13086).

Our center has experience with inhaled allergen challenge with house dust mite (*D. farinae*) using identical methods for challenge procedures. We currently hold an IND (#13086, PI: [name]) for use of inhaled house dust mite extract for allergen challenge in allergic asthmatic adults.

At the doses proposed in this study, the most significant predictable risk to subjects as a result of allergen inhalation is development of immediate airway obstruction (bronchospasm) during the EPR, which would cause shortness of breath, cough and/or wheeze. This drop in FEV₁ during the EPR should be short lived (maximal 10 to 30 minutes after allergen), and reversible with medications such as beta agonists (albuterol). This effect is similar to the effect of methacholine²¹, which is an FDA-approved agent employed for the diagnosis of airway reactivity and asthma.

Other possible risks include development of a LPR to allergen inhalation. This occurs in approximately 50% of asthmatics challenged, consisting of similar symptoms described for the EPR. Since a key endpoint of this study is to identify which subjects have a LPR, albuterol for rescue prior to the 10 hour post challenge time point will only be employed if the FEV₁ does not show spontaneous improvement, and/or if the subject has distress necessitating rescue. All subjects will be given 4 puffs of albuterol at 10 hours after the inhaled allergen challenge.

There is an infrequent risk of an asthma exacerbation after the dust mite challenge. Subjects will be monitored until the exacerbation is resolved and will be treated as clinically appropriate.

There are no expected benefits from inhalation of cat allergen extract.

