9.3. Risks to Subjects

At the doses proposed in this study, the most significant predictable risk to subjects as a result of allergen inhalation is development of immediate airway obstruction (bronchospasm) during the EPR, which would cause shortness of breath, cough and/or wheeze. This drop in FEV₁ should be short lived (maximal 10 to 30 minutes after allergen) and reversible with medications such as beta agonists (albuterol). This effect is similar to the effect of methacholine, which is an FDA-approved agent employed for the diagnosis of airway reactivity and asthma.

Other possible risks include development of a LPR to allergen inhalation. This occurs in approximately 50% of asthmatics challenged, consisting of similar symptoms described for the EPR. Since an important secondary endpoint of this study is to identify which subjects have a late asthmatic response, albuterol for rescue prior to the 10 hour post challenge time point will only be employed if the FEV₁ does not show spontaneous improvement, and/or if the subject has distress and requests rescue. All subjects will be given 4 puffs of albuterol 10 hours post-challenge with additional doses given based on FEV₁ and subject distress.

Sputum induction may induce cough, chest tightness or bronchospasm, and albuterol will be immediately available.

Venipuncture carries a risk of hematoma, and this procedure will be performed only by trained staff members.

There is no risk to measurement of eNO since subjects are simply asked to exhale into a mouthpiece.

Nasal ELF collection is associated with a rare risk of sneezing.

There is no known risk associated with HRV monitors or ASSIST devices. The ASSIST devices are under development and are not in clinical use, therefore no data collected from them will impact subject management

or care in this study. Heart rate, respiratory rate, blood pressure, and oxygen saturation will be monitored during the visits using standardized equipment approved for clinical use.

There is a potential risk for breach of confidentiality and privacy.

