9.5. Reporting of AEs and SAEs

UNC-Chapel Hill Human Research Protection Program Standard Operating Procedures will be followed for reporting adverse events/unanticipated problems to the Biomedical IRB and NC TraCS DSMB. All SAEs will be reported to the CBER of the FDA as well as to the UNC OHRE, DSMB, and the NIH sponsor within 24 hours of recognition of the event, including the filing of an IND safety report. Adverse events will be reported to both the FDA, UNC IRB, and DSMB on no less than a quarterly basis, or when the protocol is completed. If criteria for suspension of the protocol are met, then the FDA and UNC IRB will be notified within 24 hours.

All subjects with a non-fatal SAE will be evaluated medically by a study physician, in concert with their own physician as appropriate. Likewise, all subjects with an adverse event will be examined and evaluated by a study physician. All assessments will include the same lung function and vital sign assessments outlined for challenge observation. Other assessments will be undertaken as needed. Any unspecified event, which in the judgment of the PI of the study, constitutes an unusual, unexpected or prolonged event (greater than 96 hours) will be reported to both the FDA, the UNC IRB, and the NC TraCS DSMB.

Failure to meet the following safety criteria would result in suspension of the study pending discussion with the DSMB and UNC IRB.

1. No occurrence of any Serious Adverse Event
2. Each SAE and the events listed in 2 a-g would be reported to the FDA, IRB, and DSMB and discussed before performing subsequent challenges or enrolling further participants. In addition, no more than 20% of subjects will fail the individual safety criteria outlined below. As it is anticipated that 100 subjects will be recruited for this screening protocol, then 20 or more subjects who fail individual safety measures will result in suspension of further study until consultation with the CBER of the FDA. Additionally, in order to further monitor safety, we will assess this after completion of 20 subjects, and annually.
 - a. Less than or equal to 40% decrease in FEV₁ or FVC from pre-challenge values following EPR or the LPR to cat hair allergen (the target endpoint is a $\geq 20\%$ decrease in FEV₁ from baseline during the EPR and a $\geq 15\%$ decrease in FEV₁ from baseline during the LPR).
 - b. If albuterol is employed as rescue, FEV₁ must recover to within 90% of baseline value within 20 minutes.

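### Rescue albuterol before hour 10: section 4.6 gives it on request, sections 1.3 and 9.3 restrict it, and nothing says which rule governs

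*Combined protocol and SAP*

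**What the plan says.** Four sections of the combined protocol and SAP bear on albuterol between the start of the challenge and hour 10.

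- **Section 4.6 (Rescue Medication Administration)** keeps albuterol "available at all times during the allergen challenge and throughout the study visits" and then states: "Albuterol will be administered any time the participant requests it for respiratory symptoms". It adds 4 puffs if the participant "experiences a 40% or greater decrease in FEV1 or FVC from pre-challenge values during the allergen challenge".
- **Section 1.3 (Non-Clinical and Clinical Study Findings)** says that before the 10-hour time point albuterol "will only be employed if the FEV₁ does not show spontaneous improvement, and/or if the subject has distress necessitating rescue". The reason given is that the study has to identify who has a late phase response (LPR).
- **Section 9.3 (Risks to Subjects)** repeats that restriction with a different distress condition: rescue is used only if FEV₁ "does not show spontaneous improvement, and/or if the subject has distress and requests rescue".
- **Section 5.1 (Allergen challenge procedure)** leaves the need for medication to the responsible physician, judged on lung function and symptoms, with no threshold.

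Sections 4.8 and 9.5 contain a 40% limit of a different kind. It is a safety criterion worded as "Less than or equal to 40% decrease in FEV₁ or FVC from pre-challenge values following EPR or the LPR to cat hair allergen". Failing it makes the subject a screen failure for the anakinra studies (4.8) and counts towards suspension of the study (9.5).

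At hour 10 itself there is no conflict, because every subject who stays receives 4 puffs.

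**The concern.** A rule that gives albuterol whenever it is asked for and a rule that allows it only under stated conditions cannot both be followed over the same 10 hours. Which one the covering physician applies affects three things.

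- **Participant management.** The same subject, in the same state, is treated under one section and not under another.
- **Endpoints.** The primary endpoint (sections 2.1, 6.1 and 6.3) is a fall in FEV₁ of at least 15% in hours 3-10. A bronchodilator given before such a fall is recorded can prevent it from being seen, so that a late responder is classed as a non-responder. Given after a qualifying fall, it cannot undo LPR status, but it can reduce the maximum fall in %FEV₁ during the LPR, which section 6.2 lists as an outcome for the IL-1β analysis.
- **Safety criteria.** Criterion 2b in section 9.5 (recovery within 20 minutes) applies only when rescue albuterol has been given, so any rescue dose brings it into play. Criterion 2d counts rescue in the first hour after challenge only. Both criteria also appear in section 4.8 and so affect eligibility for the anakinra trials.

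**Working it through.** The point rests on no calculation. The check is to apply each section, as worded, to the same subject before hour 10.

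| Subject before hour 10 | Section 4.6 | Section 1.3 | Section 9.3 | Section 5.1 |
|---|---|---|---|---|
| A. Mild symptoms, asks for albuterol, FEV₁ recovering, no distress | Given | Not given | Not given | Physician decides |
| B. Distress that needs rescue, no request, FEV₁ recovering | No trigger met, but not forbidden | Allowed | Not given | Physician decides |
| C. No request, no distress, FEV₁ not recovering | No trigger met, but not forbidden | Allowed | Allowed | Physician decides |

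**Subject A** is a direct contradiction. Section 4.6 attaches no condition on FEV₁ or distress to a request, while 1.3 and 9.3 exclude everything outside their conditions. A request cannot simply be read as evidence of distress, because 9.3 names the two separately and asks for both.

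**Subject B** is a narrower contradiction, between 1.3 and 9.3. Section 1.3 accepts distress alone ("if the subject has distress necessitating rescue"). Section 9.3 wants distress together with a request. Section 4.6 is silent here, since it says when albuterol is given and does not limit it to those cases.

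**Subject C** shows no contradiction. Rescue is open under 1.3 and 9.3, and 4.6 does not forbid it.

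**Scope of the 40% trigger in section 4.6.** Two readings are possible.

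- *Dosing period only.* Section 4.6 names the challenge separately from the study visits, and section 5.1 starts post-challenge monitoring once the challenge has been stopped.
- *The longer challenge day.* Sections 2.2 and 6.2 describe one blood sample as taken during the challenge, but section 4.2 schedules the challenge-day sample at 10 hours, or after the 2-hour observation for subjects who leave early. The document therefore also uses the phrase loosely.

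The text does not settle which reading applies to the trigger.

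**The case against.** The best defence is that section 5.1 puts the decision with a physician, that section 5.1 also has the supervising physician physically present throughout the challenge procedure, and that albuterol is always at hand. No section bars rescue for a subject who is deteriorating. Sections 1.3 and 9.3 describe background and risk, and a careful physician would probably take 4.6 as the operating instruction. This limits the practical harm. It does not remove the contradiction: 5.1 adds a further rule without saying that it overrides the others, and 1.3 and 9.3 are worded as restrictions on conduct.

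Three stronger readings are tempting, and the documents do not support them.

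- *A late fall above 40% breaches the safety limit yet would go untreated.* The limit in 4.8 and 9.5 decides screen failure and suspension. It is not a treatment rule, and its scope need not match that of the trigger in 4.6. Lack of recovery in FEV₁ permits rescue under 1.3 and 9.3, and the physician may act under 5.1. FEV₁ is also measured on a schedule up to hour 10, so recovery is measured, although the criterion for it is not defined.
- *Any rescue in hours 3-10 corrupts the primary endpoint and the rescue count.* Rescue after a recorded fall of at least 15% in the window leaves LPR status unchanged, and criterion 2d does not count doses after the first hour.
- *About 25 of 100 subjects are affected.* This multiplies 100 screened subjects by the 25% rescue rate in section 6.4 (0.25 × 100 = 25). That rate is a planning figure for the anakinra trials, which enrol selected late responders. Using the numbers that 6.4 expects among those screened, the same rate would give 0.25 × 50 = 12.5 subjects with an early response, or 0.25 × 25 = 6.25 with a late one. Even these would count rescues, not rescues on which the sections disagree.

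**Conclusion.** The concern holds. Section 4.6 contradicts sections 1.3 and 9.3 on rescue at request before hour 10. Sections 1.3 and 9.3 also differ from each other on whether distress needs a request, and 5.1 adds physician discretion without an order of precedence. This is a conflict between stated rules, not a missing detail.

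The statistical exposure is specific. Rescue before a fall of at least 15% is recorded in hours 3-10 can mask the primary endpoint, and later rescue can reduce the maximum LPR fall. Any rescue dose activates criterion 2b, and a dose in the first hour also counts towards 2d. This assumes only that albuterol, a bronchodilator, raises FEV₁. How many subjects would be handled differently cannot be derived from the documents.

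The unclear period of the 40% trigger is a secondary point. It needs to be stated, but it does not show that large late falls go untreated.

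**What to change.** The sponsor must reconcile sections 1.3, 4.6, 5.1 and 9.3 into one consistent rescue rule, written once and cross-referenced from the other sections. The rule should settle:

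- whether a participant's request is sufficient by itself;
- whether distress without a request is sufficient;
- how absence of recovery is judged from the scheduled spirometry;
- how physician discretion relates to the rest;
- the period over which the 40% trigger in 4.6 applies.

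Which answers are clinically right is for the sponsor, and none is proposed here.

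On the case report form, record the time of each rescue dose and the trigger that was met. The discharge worksheet mentioned in section 9.5 already captures the safety criteria, but the protocol does not say that it records the trigger for each dose. With that record, the analyst can see whether rescue came before or after a qualifying fall.

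The cost is protocol wording and one line on the form.
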